#### **Between Visits 1 and 2:**

##### ***Heartsight Intervention Package 1 (Understanding Cardiac Arrest):***

After completion of the baseline survey, participants assigned to the intervention arm will be emailed login and access details for their Heartsight account using [this email script](#). Intervention arm participants who do not access Heartsight within 4 days of receiving access details will be sent a reminder email (also included in email script). Log the date the package is issued and when the reminder email is sent, if needed, under [“ALL Participants RESURFACE”](#).

Participants assigned to the control arm will not receive any materials.

##### ***Heartsight Intervention Package 2 (Preparing for Discharge):***

Study coordinators will monitor EPIC to determine when intervention arm participants have moved to the floor. At this time, intervention arm participants will be emailed access details for the Preparing for Discharge package of Heartsight articles using [this email script](#). Intervention arm participants who do not access Heartsight within 4 days of receiving Preparing for Discharge access details will be sent a reminder email. Log the date the package is issued and when the reminder email is sent, if needed, under [“ALL Participants RESURFACE”](#).

Participants assigned to the control arm will not receive any materials.

#### **Visit 2 (Discharge):**

##### ***Survey 2 (Discharge, 15 min):***

Study coordinators should check EPIC each morning to determine when participants will be discharged from the hospital. Approximately one day before discharge, study coordinators should approach participants on the floor.

Before approaching, check User Insights to see whether the participant is a low- or no-use participant (accessed <25% of previous Heartsight package). If so, include the low- or no-use questions in addition to the discharge survey in the packet of materials for the participant.

Leave the discharge survey in the correct language (English or Spanish) with the participant to complete. Schedule a time to pick up the completed discharge

survey. At the scheduled time, return to pick up the survey, enter the responses into REDCap, and file the paper survey in the NeuroCardiac Care office.

If the participant has indicated they would prefer to complete the survey on REDCap instead, the study coordinator should click into the “Subjective Discharge” instrument in their REDCap record. If the participant is a low- or no-use participant, click the corresponding radio button, and save. Then click back into the record and switch “Ready to send?” to yes. Save, exit, click back into the record, navigate to “Survey Options,” and open “Survey Access Code + QR Code.” Copy and paste the survey link and code into an email from [[contact]](mailto:[contact]). Confirm verbally with the participant that they have received the email (if not, ask them to check their spam inbox).

The study coordinator should also leave a GENEActiv device, study log, stamped envelope for return, and [instructions for proper use and return in 1 week](#) with the participant. Remind the participant that the study team can be reached at [[contact]](mailto:[contact]) or [contact] if any questions about using or returning the GENEActiv come up.

Once the discharge survey has been completed, study coordinators should also process the first \$50 payment to the participant through TruCentive.

Log dates of discharge survey completion and first payment under [“ALL Participants RESURFACE.”](#)

### **Between Visits 2 and 3:**

At 1 week post-discharge, study coordinators will call participants to remind them to return the GENEActiv, following [this phone script](#). Log date of call under [“ALL Participants RESURFACE.”](#)

The study coordinator should check in with the PACE team whenever a GENEActiv is expected to be returned. Only when the PACE team has confirmed that a participant’s GENEActiv has been returned should the second payment of \$25 be processed. Log dates of GENEActiv return and second payment under [“ALL Participants RESURFACE.”](#)

### ***Heartsight Intervention Package 3 (Focusing on You):***

One month after hospital discharge, intervention arm participants will be emailed access details for the Focusing on You package of Heartsight articles using [this email script](#). Participant utilization of Heartsight will be tracked using User Insights. Intervention arm participants who do not access Heartsight within one month of receiving Focusing on You access details will be sent a reminder email, also following the email script linked above. Log the date the package is issued and when the reminder email is sent, if needed, under [“ALL Participants RESURFACE.”](#)

Participants assigned to the control arm will not receive any materials.

**Visit 3 (Final):**

***Survey 3 (Final, 20 min):***

Three months after hospital discharge, study coordinators will call participants to schedule the final survey using [this phone script](#). Be sure to check which arm the participant is in to obtain the correct version of the survey.

If the participant prefers REDCap, the study coordinator should click into the “Subjective 3-Month” instrument in their REDCap record. If the participant is a low- or no-use participant, click the corresponding radio button and save. Then re-open the instrument, switch “Ready to send?” to yes, save, and exit. Re-open the instrument, click “Survey Options,” and open “Survey Access Code + QR Code.” Copy and paste the survey link and code into an email from [[contact]](mailto:[contact]). Confirm with the participant that they have received the email (if not, ask them to check their spam inbox).

If the participant prefers a phone call, the study coordinator should either fill out the REDCap directly while on the call or fill out the paper survey, enter responses into REDCap, and file the paper survey in the NeuroCardiac Care office.

Once the 3-month survey has been completed, study coordinators should process the final \$50 payment to the participant through TruCentive.

Log dates of final survey completion and final payment under [“ALL Participants RESURFACE.”](#) At this point, surrogates’ participation in the study is considered complete. Remove them from the “CURRENT Participants RESURFACE” tab and mark them as complete under “ALL Participants RESURFACE > Study Status.”

**b. Data Collection, Management, and Analysis**

**i. Data Collection Methods**

Study coordinators will conduct surveys via paper copies, phone, or REDCap, depending on the participant’s preferences. All survey responses will be entered into REDCap, and any paper copies will be filed in the NeuroCardiac Care office.

**Survey 1 (Baseline):**

- a. Demographics
- b. Threat Perception Survey (TPS)
- c. Intolerance of Uncertainty Scale (IUS)
- d. Mishel Uncertainty in Illness Scale - Family Member (MUI/PPUS-FM)
- e. PTSD Checklist (PCL-5)
- f. Presence at cardiac arrest

**Survey 2 (Discharge):**

- a. (If no-/low-use) No- or low-use questionnaire
- b. Subjective perception of uncertainty
- c. Mishel Uncertainty in Illness Scale - Family Member (MUI/PPUS-FM)
- d. PTSD Checklist (PCL-5)
- e. Cardiac Anxiety Questionnaire (CAQ)
- f. Enriched Social Support Instrument (ESSI)

**Survey 3 (3 Months Post-Discharge):**

- g. (If no-/low-use) No- or low-use questionnaire
- h. Subjective perception of uncertainty
- i. Mishel Uncertainty in Illness Scale - Family Member (MUI/PPUS-FM)
- j. PTSD Checklist (PCL-5)
- k. Cardiac Anxiety Questionnaire (CAQ)
- l. Zarit Burden Interview – 12-item short form
- m. (If intervention arm) Heartsight feedback

**GENEActiv Data:** bin files and csv files.

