## c. Study Design

This study is a two-arm unblinded RCT in which up to 100 adult CA surrogates will be enrolled over a 1-year period and randomized (using a 2:1 allocation until at least 30 intervention arm participants have completed their study participation) to either receive the Heartsight intervention or no additional information beyond usual treatment (control group). Data collection will occur at the initial approach in the ICU, on the floor, and at 3 months post-discharge. All participants will be English- and/or Spanish-speaking. If a CA patient dies at any point in the protocol, their surrogate is no longer eligible to continue in the study.

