### **Visit 2 (Discharge):**

#### ***Survey 2 (Discharge, 15 min):***

Study coordinators will monitor the electronic medical record to determine when participants will be discharged from the hospital. Approximately one day before discharge, study coordinators will approach participants to deliver the second survey. This survey, taken by participants in both arms, can be completed asynchronously in-person (on paper) or via REDCap (online). The discharge survey will contain questions about subjective perception of uncertainty (3 questions), illness uncertainty (Mishel Uncertainty in Illness Scale for Family Members, 31 questions), PTSS (PCL-5, 20 questions), cardiac anxiety (Cardiac Anxiety Questionnaire fear subscale, 8 questions), and social support (Enriched Social Support Instrument, 6 questions). Intervention arm participants who have been identified as viewing less than 25% of the Preparing for Discharge articles will receive two additional questions asking for user feedback.

Upon completion of the discharge survey, study coordinators will process the first \$50 payment to the participant. At this time, study coordinators will also provide all participants with a GENEActiv device, study log, stamped envelope for return, and instructions for proper use and return in 1 week.

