### **Visit 3 (Final):**

#### ***Survey 3 (Final, 20 min):***

Three months after hospital discharge, study coordinators will call participants to schedule the final survey. This survey, taken by all study participants, can be completed via REDCap (online) or over the phone. The final survey will contain

questions about subjective perception of uncertainty (3 questions), illness uncertainty (Mishel Uncertainty in Illness Scale for Family Members, 31 questions), PTSS (PCL-5, 20 questions), cardiac anxiety (Cardiac Anxiety Questionnaire fear subscale, 8 questions), and caregiver burden (Zarit Burden Interview, 12 questions). Intervention arm participants who have been identified as viewing less than 25% of the Focusing on You articles will receive two additional questions asking for user feedback. All intervention arm participants will also receive a Heartsight feedback survey (23 questions).

Upon completion of the final survey, study coordinators will process the final \$50 payment to the participant. At this point, surrogates' participation in the study is considered complete.

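### The no-/low-use questions, which only low-use intervention participants receive, are listed ahead of the outcome scales in Surveys 2 and 3 and should come after them

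*Combined protocol and SAP*

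**What the plan says.** Section 3.b.i (Data Collection Methods) gives lettered contents for each survey. Survey 3 opens with "If no-/low-use) No- or low-use questionnaire". Subjective uncertainty, the Mishel scale, PCL-5, CAQ and the Zarit form follow, and Heartsight feedback (intervention arm only) is last. Survey 2 likewise opens with the no-/low-use form, ahead of subjective uncertainty, Mishel, PCL-5, CAQ and ESSI.

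Section 3.a.ix (Study Measurements and Protocol) says who receives the form. At discharge: "Intervention arm participants who have been identified as viewing less than 25% of the Preparing for Discharge articles will receive two additional questions". At 3 months: "Intervention arm participants who have been identified as viewing less than 25% of the Focusing on You articles will receive two additional questions".

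Section 3.a.x (Visit Procedures) describes the REDCap route. Within the Subjective Discharge instrument, the coordinator is told: "If the participant is a low- or no-use participant, click the corresponding radio button, and save". The coordinator then marks the survey ready and copies the survey link into an email. The 3-month steps are parallel and use the Subjective 3-Month instrument.

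On mode, the final survey "can be completed via REDCap (online) or over the phone", as the participant prefers. Coordinators log the dates of completion and payment. No section asks them to record the mode.

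**The concern.** Uncertainty, cardiac anxiety and PTSS are all self-rated, and answers to such scales can depend on what was asked just before. A participant first asked about not having used an information site, and then asked how uncertain they feel, may answer differently from one who meets the uncertainty items cold. Here that prompt can reach only one arm.

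The estimates exposed are those of Exploratory Aims 1a and 1b (3-month arm differences in uncertainty, CAQ and PCL-5) and Exploratory Aim 1c (lagged associations, which also use discharge scores). Section 3.b.iii (Statistical Methods) intends the lower bounds of the correlations for sizing the larger study, so an artefact could carry forward.

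The analysis could not repair it afterwards. As planned, every identified low user receives the questions and nobody else does, so an order effect cannot be separated from being a low user. Dropping low users would break the randomized comparison.

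**Working it through.** The plan gives no figure on this point, so the main check sets the sections side by side. A short calculation then puts the possible size in proportion.

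**1. Who can receive the questions.** Section 3.a.ix restricts them to intervention participants below 25% of a package. Section 3.a.vii gives 7 articles for Preparing for Discharge and 12 for Focusing on You. Since 0.25 × 7 = 1.75 and 0.25 × 12 = 3, the rule catches those who viewed at most 1 and at most 2 articles respectively. The group is part of the intervention arm and none of the control arm.

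**2. Where the questions appear.**

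| Source | What it shows about order |
|---|---|
| 3.b.i, Surveys 2 and 3 | Listed first, directly before subjective uncertainty |
| 3.a.x, REDCap steps | Low-use flag set in the Subjective instrument, from which the survey link is sent |
| 3.a.ix, Visits 2 and 3 | Mentioned after the scales, as additional questions; no order stated |
| 3.a.x, Visit 2 paper packet | Included with the discharge survey; no position stated |

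The first two rows point the same way and the last two are silent on order. The listed order is therefore probably the real one for REDCap, and it is unspecified on paper.

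**3. Size relative to sampling error.** The 95% half-width for a difference in means, in SD units, is 1.96 × √(1/n₁ + 1/n₂).
- 30 intervention completers (section 3.a.iii), with 15 controls implied by 2:1: 1.96 × √(1/30 + 1/15) = 0.62 SD.
- The full allocation table, 67 and 33 (section 3.a.viii): 1.96 × √(1/67 + 1/33) = 0.42 SD.

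If a share f of the intervention arm receives the questions and their scores move by d SD, the arm mean moves by f × d. Neither f nor d is in the documents. The value of d needed for the shift to equal the half-width is d = half-width / f. Taking f from 0.2 to 0.5 as an assumption:
- f = 0.5: 0.42 / 0.5 = 0.84 SD, or 0.62 / 0.5 = 1.24 SD.
- f = 0.2: 0.42 / 0.2 = 2.1 SD, or 0.62 / 0.2 = 3.1 SD.

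Two preceding questions would need a very large effect to match the sampling error. That supports calling the bias probably smaller than the noise. It does not estimate the bias.

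**The case against.** The strongest reply is that the lettered lists are inventories and not scripts. Nothing says the letters give the order of presentation, section 3.a.ix describes the scales first, and a flag set by staff does not show where the questions appear on screen. This stands as a limit on certainty. It does not remove the point: the REDCap steps agree with the lists, and if the real order differs, the lists need a clarifying edit anyway.

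It is also fair that only exploratory estimates are touched. The thresholds in section 3.b.iii concern recruitment, retention and scale completion, and none rests on an arm difference in uncertainty, CAQ or PCL-5. Actigraphy sleep duration is unaffected.

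Two stronger readings are tempting and should not be drawn.

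- **That outcomes are collected differently by arm in general.** They are not. The scales, their timing and the choice of modes are the same in both arms. The difference is two questions for low users.
- **That arm-aware phone interviewing is a separate flaw.** Coordinators are told: "Be sure to check which arm the participant is in to obtain the correct version of the survey". But section 2.c declares the design openly: "This study is a two-arm unblinded RCT in which up to 100 adult CA surrogates will be enrolled". Participants rating themselves know whether they received Heartsight, and coordinators randomize them. Checking the arm adds little. Phone is a Survey 3 option open to both arms, and its expected share is not given. Restricting phone to non-responders would tie mode to non-response and could work against the 80% retention criterion. Recording the mode is enough.

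**Conclusion.** The point holds as a minor, avoidable weakness in instrument order. It rests on two things: that the lists in section 3.b.i reflect the order in which questions are presented, which is probable but not stated, and that the two questions, described only as seeking user feedback from low users, prompt thought about non-use. Their wording is not in the documents.

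The direction of any shift is unknown and its size cannot be estimated from the documents. It would act on part of one arm, is probably smaller than the sampling error, and would persist however many participants are enrolled. Only Exploratory Aims 1a to 1c are exposed. Question order is worth settling even in an unblinded pilot because, unlike knowledge of arm, it is fully within the study team's control.

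**What to change.** 1. In section 3.b.i, move the no-/low-use form below all the scales: after ESSI in Survey 2, and after the Zarit form but before Heartsight feedback in Survey 3. Heartsight feedback stays last, as it already is.
2. Match this in the REDCap build, so that the flag shows the two questions only after the scales, and in the order of the paper packet and phone form. Add one sentence to sections 3.a.ix and 3.a.x, for example: *No-/low-use questions are presented after all outcome scales have been completed.*
3. Add a field for Survey 3 mode (REDCap or phone) and report it by arm. Leave the participant's choice of mode as it is.

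The cost is a reordering of forms, a small REDCap edit and one extra field. No staff are added, and no usage question is removed. The protocol lists the study as not yet recruiting. If the change is made before launch, everyone meets the scales in the same order. If enrollment has begun, record the date of the change.

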**ii. Data Management**

Statistical analyses will be led by [name], MPH. He has been involved from the earliest stage of pilot study planning to ensure that rigorous statistical analyses are planned.

Data management will be led by the CBCH Data Team. They use proven tools that have been successful in other trials conducted by CBCH, all of which integrate with REDCap.

A posting on clinicaltrials.gov will be made to summarize the details of the study protocol. At the end of the study procedures, the publicly available clinicaltrials.gov posting will be updated with a summary of enrollment data and key results at the end of the trial.

**iii. Statistical Methods**

**Statistical approach for Aim 1:** *Enroll up to 100 (until 30 in the intervention arm) surrogates of CA patients to (Aim 1a) pilot recruitment and randomization procedures, (Aim 1b) estimate retention rate at 3 months, and (Aim 1c) assess the engagement and utilization metrics through the app for frequency of access and time spent on packages.*

**Aim 1a.** Based on our prior studies with surrogates of CA patients who survive to hospital discharge, 8 surrogates/month will be eligible to participate in the proposed study and <5 participants/month will be considered not meeting the outcome. **Aim 1b.** Based on our prior successes, we expect retention rates of ~90%. Since this is an

interventional study, the proportion of participants who complete the 3-month assessments <80% will be considered as not meeting the outcome. A sample size of  $N = 30$  surrogates results in a 95% confidence interval of this estimate equal to 79% – 100%, providing sufficient precision for study planning. **Aim 1c.** Acceptability will be assessed by recording reasons for dropout, reasons for noncompliance, and querying participants about burden at 3 months. We will consider scale completion >90% acceptable. The application can track the utilization of the content, time spent on each module of the packages, and participants' review and content feedback.

**Statistical approach for Exploratory Aims 1a-c.** *Estimate the association of intervention v. control with the surrogate's uncertainty levels at 3 months post-discharge (Exploratory Aim 1a), cardiac anxiety, and PTSS at 3 months post-discharge (Exploratory Aim 1b), and explore the lagged associations of uncertainty with cardiac anxiety and PTSS (Exploratory Aim 1c).* We will compute 95% bootstrap confidence intervals around the mean difference in **(1a)** uncertainty in illness total scores; **(1b)** total scores on the cardiac anxiety questionnaire and PCL-5 between intervention and control conditions and **(1c)** the associations between surrogates' uncertainty scores and cardiac anxiety as well as PTSS accounting for enrollment, discharge, and 3 month scores. The lower bounds of these correlations will be used for sample size calculations when planning the larger study to account for uncertainty in small samples.  $N = 30$  has been recommended as sufficient for pilot studies.

**Statistical approach for Exploratory Aim 2:** *Obtain a preliminary estimate of the association of intervention v. control with surrogates' sleep duration within the first one week after hospital discharge.* We will compute 95% bootstrap confidence intervals around the mean difference in duration of sleep over the one week post-discharge, between intervention and control participants.

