### iii. Sample Size

We plan to enroll up to 100 adult surrogates of CA patients in this study. All participants will be English and/or Spanish speakers. Participants will be enrolled and randomized (using a 2:1 allocation) to either the active informational intervention or the care as usual control group. Enrollment will end once 30 participants in the intervention arm have completed their participation in the study.

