#### **viii. Randomization**

[name] will be responsible for generating the randomization allocation table for the REDCap randomization module, which will assign participants to arms.

Method:

1. Before study launch, [name] will build a master randomization allocation table using Excel. This allocation table will yield arm assignments for 100 study participants (67 in the intervention arm, 33 in the control arm).
2. [name] will upload the allocation table to the REDCap randomization module.
3. Once the study launches, REDCap will switch to production mode, and the randomization module will be locked. Randomization assignments cannot be changed going forward.

4. When a new participant is recruited, study coordinators will click “Randomize” for a new record in REDCap. This will yield the arm assignment for the new participant, as determined by the pre-made allocation table.

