**ix. Study Measurements and Protocol**

**Visit 1 (Baseline):**

***Survey 1 (Baseline, 20 min):***

Once written consent has been obtained, a study coordinator will use the REDCap randomization module to assign the participant to a study arm. All participants, regardless of randomization, will receive a baseline survey that they can complete asynchronously in-person (on paper) or via REDCap (an online, HIPAA-compliant data collection tool that can be sent via email). The baseline survey will contain questions about participant demographics (22 questions), threat perception (Threat Perception Survey, 7 questions), uncertainty intolerance (Intolerance of Uncertainty Scale, 27 questions), illness uncertainty (Mishel Uncertainty in Illness Scale for Family Members, 31 questions), PTSS (PCL-5, 20 questions), and the surrogate’s presence during their loved one’s cardiac arrest (4 questions).

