**Between Visits 1 and 2:**

***Heartsight Intervention Package 1 (Understanding Cardiac Arrest):***

After completion of the baseline survey, participants assigned to the intervention arm will be emailed login and access details for their Heartsight account. These participants will be instructed to view the Understanding Cardiac Arrest package of articles, which provides information about cardiac arrest and the ICU, and provide article-specific feedback by leaving comments on the website. Participant utilization of Heartsight will be tracked using User Insights. Intervention arm participants who do not access Heartsight within 4 days of receiving access details will be sent a reminder email.

Participants assigned to the control arm will not receive any materials.

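### The 3-month arm differences in uncertainty and PTSS carry no baseline adjustment, although both scales are collected at enrolment

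*Combined protocol and SAP*

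**What the plan says.** Section 3.b.iii (Statistical Methods) sets the analysis for Exploratory Aims 1a to 1c in one sentence. It opens "We will compute 95% bootstrap confidence intervals around the mean difference in" and lists (1a) uncertainty totals and (1b) cardiac anxiety and PCL-5 totals, compared between arms at 3 months. No covariate, change score or model is named. Enrolment scores appear only under (1c), where the associations between scales are estimated "accounting for enrollment, discharge, and 3 month scores".

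The baseline survey (section 3.a.ix, Visit 1) includes "illness uncertainty (Mishel Uncertainty in Illness Scale for Family Members, 31 questions), PTSS (PCL-5, 20 questions"). Both scales are repeated at discharge and at 3 months. Cardiac anxiety is not in the baseline survey; it first appears at discharge: "cardiac anxiety (Cardiac Anxiety Questionnaire fear subscale, 8 questions), and social support".

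Two statements bound the size of the analysis. Section 3.a.iii: "Enrollment will end once 30 participants in the intervention arm have completed their participation in the study". Section 3.a.viii: "This allocation table will yield arm assignments for 100 study participants (67 in the intervention arm, 33 in the control arm").

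On timing, section 3.a.ix says: "Once written consent has been obtained, a study coordinator will use the REDCap randomization module to assign the participant to a study arm". The baseline survey follows, and then: "After completion of the baseline survey, participants assigned to the intervention arm will be emailed login and access details for their Heartsight account".

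**The concern.** Section 2.b promises preliminary estimates of the intervention's association with uncertainty and PTSS at 3 months. At pilot size these intervals will be wide. A participant's enrolment score on the same scale is the most obvious predictor of the 3-month score, and the trial collects it anyway. Leaving it out of the arm comparison has two consequences:

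- The interval is wider than it need be if the two scores are at least moderately correlated.
- A chance baseline difference of d SD between arms moves the raw estimate by about r × d SD. The raw interval allows for this over repeated randomisations, but adjustment removes it from the trial actually run. Section 3.a.viii describes no stratification on baseline scores that would limit such a difference.

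The Aim 1 criteria on recruitment, retention and scale completion are not at stake. The one stated planning use, the lower bounds of the correlations, most naturally refers to (1c).

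**Working it through.** **The plan's own precision figure.** The only one is for retention: 90% with N = 30, 95% interval 79% to 100%. The Wald formula gives 0.90 ± 1.96 × √(0.9 × 0.1 / 30) = 0.793 to 1.007, which reproduces it after truncation at 100%. No SD, effect size or interval width is given for the 3-month arm differences, so what follows is in SD units.

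**Inputs.**
- Completers: 30 intervention (stopping rule, 3.a.iii) and about 15 control under 2:1 with similar retention, which is roughly the minimum; 67 v 33 (full allocation table, no dropout) as the maximum; 45 v 22 and 60 v 30 as illustrative sizes between.
- Correlation r between baseline and 3-month scores: not in the documents; assumed 0.3, 0.5 and 0.7, with 0 as the worst case shown.

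**Formulas**, with N = n1 + n0:
- Unadjusted half-width = t(N−2) × √(1/n1 + 1/n0)
- Adjusted half-width = t(N−3) × √(1/n1 + 1/n0) × √(1 − r²) × √(1 + 1/(N−4))

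For 30 v 15, √(1/30 + 1/15) = 0.316. Unadjusted: 2.017 × 0.316 = 0.638. Adjusted at r = 0.5: 2.018 × 0.316 × 0.866 × 1.012 = 0.559.

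| Completers | Unadjusted | r = 0 | r = 0.3 | r = 0.5 | r = 0.7 | Break-even r |
|---|---|---|---|---|---|---|
| 30 v 15 | 0.638 | 0.646 | 0.616 | 0.559 | 0.461 | 0.16 |
| 45 v 22 | 0.520 | 0.524 | 0.500 | 0.454 | 0.374 | 0.13 |
| 60 v 30 | 0.444 | 0.447 | 0.426 | 0.387 | 0.319 | 0.11 |
| 67 v 33 | 0.422 | 0.424 | 0.405 | 0.367 | 0.303 | 0.10 |

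At r = 0.5 and 30 v 15 the equivalent increase in sample size is (0.638/0.559)² = 1.30.

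**Check with the planned type of interval.** Percentile bootstrap intervals were simulated at 30 v 15 with normal scores (1,000 trials, 500 resamples within arm). The ratio of adjusted to unadjusted width was 1.014, 0.967, 0.878 and 0.718 at r = 0, 0.3, 0.5 and 0.7. The adjusted interval was narrower in 37%, 65%, 91% and 99.9% of trials. Coverage was about the same for both (roughly 0.91 to 0.94). Absolute half-widths are smaller than the t-based ones (about 0.59 unadjusted), but the relative gains agree.

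**Chance imbalance.** The baseline difference has standard error √(1/n1 + 1/n0) SD. The probability that it exceeds 0.3 SD in either direction is 34% at 30 v 15 (0.3/0.316 = 0.95), 25% at 45 v 22, 18% at 60 v 30 and 16% at 67 v 33. A 0.3 SD imbalance moves the raw estimate by 0.3 × r = 0.09, 0.15 or 0.21 SD at r = 0.3, 0.5 or 0.7.

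**The case against.** **The gain rests on an assumed r.** Baseline is taken in the ICU and the outcome three months after discharge, so a moderate r cannot be taken for granted. This stands. At r = 0.3 and 30 v 15 the gain is small: 3% in the simulation above, and almost nothing (about 0.59 to 0.59) in a separate run of 600 trials. But the risk is one-sided, since the cost at r = 0 is about 1% in width.

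**These are exploratory estimates in a feasibility pilot.** Even 0.56 SD is too wide to fix an effect size, and no stated decision turns on it. This also stands, and it limits the point to an inexpensive improvement.

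**The plan is silent and does not rule adjustment out.** True, but a mean difference with no covariate named reads as unadjusted. If adjustment is meant, the same added wording settles it.

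**Completers are a selected group.** Surrogates leave if the patient dies (section 2.c), and about 10% loss is expected, so calling the raw difference unbiased needs a missing-data assumption. That is right, but it applies to both estimates.

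**The covariate is collected after randomisation in an unblinded trial.** This is the most substantive objection. Missing baselines could differ by arm, and Package 1 goes out only after the baseline survey is completed. However, that email is the first described contact that reveals the arm, so no bias is shown. With 10% of baselines missing and mean-imputed, the simulated half-widths at 30 v 15 were 0.58, 0.52 and 0.45 at r = 0.3, 0.5 and 0.7. With random missingness of 5% in one arm and 25% in the other, there was no visible bias and most of the gain remained. These runs do not cover missingness related to the outcome.

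**Conclusion.** The point holds. Exploratory Aims 1a and 1b specify plain mean differences for two outcomes whose enrolment values are already collected. This is avoidable loss of precision, not an error. At 30 v 15 completers, adjustment shortens the interval by about 3%, 12% or 28% at r = 0.3, 0.5 or 0.7 and lengthens it by about 1% at r = 0. The proportions are similar at larger sizes. The size of the gain depends on an r that the documents do not give, so confidence in it is moderate; the direction is clear once r exceeds about 0.16 to 0.2 at the smallest size, or 0.10 at 67 v 33. The point does not extend to cardiac anxiety, whose first measurement comes after the first two packages may have been sent.

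**What to change.** In section 3.b.iii, for MUIS-FM and PCL-5:

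- Make the main estimate the arm coefficient from a linear model of the 3-month score on arm and the same scale's baseline score, with a 95% bootstrap interval resampling within arm.
- Keep participants without a baseline score by imputing the overall mean of the covariate, not an arm-specific mean.
- Report the raw mean difference as secondary, and the observed r for each scale, which the larger study will need.
- Leave cardiac anxiety unadjusted; its discharge score should not serve as a baseline.

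To protect the covariate, state in section 3.a.ix that the arm is not disclosed until the baseline survey is returned. Alternatively, randomise only after its return, still counting consented non-returners in the recruitment figures.

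**Cost.** Two sentences of SAP text and a small code change, with no new data. The non-disclosure sentence needs no system change. Moving randomisation would require adapting the REDCap step in section 3.a.x, where the arm-specific record is created at randomisation. Package 1 already waits for the baseline survey, so neither option delays it.
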